## 9.6 Safety Analyses

### 9.6.1 Analyses of Primary Safety Endpoint(s)

All the safety analysis will be performed based on full analysis set unless otherwise specified.

Table 4. Safety Endpoint Summary Table

Endpoint	Statistical Analysis Methods
Incidence of Dose-Limiting Toxicities (DLTs), treatment-related and treatment-emergent adverse events, and clinically significant changes in vital signs, electrocardiograms (ECGs), and clinical laboratory tests	

Treatment-emergent, treatment-related adverse events, vital signs, electrocardiograms, clinical laboratory tests will be performed based on full analysis set.

Incidence of dose-limiting toxicities will be based on DLT evaluable analysis set.

### 9.6.2 Adverse Events

The Medical Dictionary for Regulatory Activities (MedDRA) version **26.1** or later will be used to code all events categorized as adverse events or disease related events to a

system organ class and a preferred term. The severity of each adverse event will be graded using CTCAE version 4.0.

Subject incidence of all treatment-emergent adverse events, serious adverse events (SAEs), grade 3 or higher, treatment-related, serious treatment-related, adverse events leading to withdrawal of investigational product, and fatal adverse events will be tabulated by system organ class and preferred term by dose level. The event categories of adverse event and disease related event both will be included.

For subjects who experienced COVID-19, SAEs on or after COVID-19 onset will be summarized.

Subject incidence of DLTs will be summarized by preferred term and dose level using the DLT Evaluatable Analysis Set. **Summary table may not be generated if the number of events is less than 5 in each cohort. The individual subject-level data will be provided.** Similar summaries will also be provided to events of interest. A listing of death will be provided.

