6.1 Treatment(s) Administered

The Amgen Investigational Product used in this study is AMG 176. The non-investigational products used in this study (azacitidine) may be considered investigational in some countries.

The Investigational Product Instruction Manual (IPIM), a document external to this protocol, contains detailed information regarding the storage, preparation, destruction, and administration of AMG 176.

6.1.1 Investigational Product: AMG 176

All investigational products will be administered at the research facility by a qualified staff member. A physician must be available at the time of administration of Investigational Product.

Description

AMG 176 is an anhydrous crystalline material that is a white to light brown powder, which is formulated as a sterile concentrate for solution for infusion. The solution is administered IV after dilution into an IV bag containing normal saline (0.9% sodium chloride).

Dosage Form

The AMG 176 investigational product is formulated as a sterile concentrate for solution for infusion at a concentration of 25 mg/mL in 10% w/w 2-hydroxypropyl beta-cyclodextrin, and buffered with 100 mM glycine to pH 9.0. AMG 176 is supplied as a sterile, preservative-free solution for IV infusion.

Drug Supply and Storage

AMG 176 will be supplied as either a 10 mL liquid deliverable volume in a single use (20R) glass vial or a 14.4 mL liquid deliverable volume in a single use (30R) glass vial.

The primary container closure system for the 10 mL presentation consists of a 20R borosilicate glass vial with a 20 mm elastomeric stopper, and an aluminum seal with flip-off dust cover. A single use vial containing 14.4 mL fill of 25 mg/mL AMG 176 has also been developed for use in the clinic. Additional details are provided in the IPIM.

It is recommended that AMG 176 be stored at or below 25°C, protected from light, and according to the storage and expiration information (where required) provided on the label that is affixed to the package containing the investigational product.

Dosage, Administration, and Schedule

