9.4.2.3.2 Adverse Events

The Medical Dictionary for Regulatory Activities (MedDRA) version 19.1 or later will be used to code all events categorized as adverse events or disease-related events.

Subject incidence of all treatment-emergent adverse events will be tabulated by system organ class and preferred term. Tables of fatal adverse events, serious adverse events, adverse events leading to withdrawal from investigational product or other protocol required therapies, and treatment emergent adverse events will also be provided.

Subject incidence of disease-related events, fatal disease-related events, and device-related events, if applicable, will be tabulated by system organ class and preferred term. Similar summaries will also be provided to events of interest.

Subject-level data may be provided instead of tables if the subject incidence is low.

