9.4.2.3.7 Exposure to Non-investigational Product

Descriptive statistics will be produced to describe the exposure to azacitidine. The number of cycles initiated, completed, discontinued, the duration of therapy and total dose will be summarized. Subject-level data may be provided instead of the summary if the subject incidence is low or single dose is given.

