### Investigational Product (IP)

IP is used in reference to AMG 176.

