**Exploratory analysis will be performed separately if needed.**

### **9.2 Subject Accountability**

The number and percent of subjects who are enrolled, receive investigational product, completed investigational product, discontinue from investigational product (including reasons for discontinuation), complete study, discontinue the study (including reasons for discontinuation) will be summarized by cohort. Enrollment by country and study site will be summarized.

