#### **9.6.9        Exposure to Non-investigational Product(s)**

Descriptive statistics will be produced to describe the exposure to azacitidine, itraconazole. **Number of cycles initiated, number of doses, cumulative dose, average dose delivered per day, average dose delivered per treated week, dose intensity and relative dose intensity** will be summarized.

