**10. Changes From Protocol-specified Analyses**

The study was terminated early. Synopsis CSR will be provided, and thus selected planned analyses will be performed. The following analyses will not be performed.

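### SAP 9.6.2 narrows the protocol's withdrawal table to AMG 176, so an adverse event that stops azacitidine alone appears in no withdrawal output

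*SAP*

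**What the plan says.** Protocol 9.4.2.3.2 promises tables of "adverse events leading to withdrawal from investigational product or other protocol required therapies". It also lets subject-level data replace a table when few subjects are affected.

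SAP 9.6.2 plans subject incidence, by system organ class, preferred term and dose level, of "adverse events leading to withdrawal of investigational product". SAP section 5 fixes what the term covers: "IP is used in reference to AMG 176". Protocol 6.1.2 classes azacitidine (Parts 4 and 5) and itraconazole (Part 3d) as non-investigational. Protocol 6.1 does note that "The non-investigational products used in this study (azacitidine) may be considered investigational in some countries", but that concerns local regulatory status and does not alter the SAP's definition.

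SAP section 10 reports early termination and a synopsis study report with selected analyses. Under the words "The following analyses will not be performed" it lists six items: PFS and EFS, time to response, BAX and caspase 3, events-of-interest summaries, antibody formation, and prior anticancer therapies. The withdrawal table is not among them.

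**The concern.** In Parts 4 and 5 the treatment under study is a pair of drugs, and a primary objective is the safety and tolerability of the pair. Protocol 7.1 foresees that a subject may stop one protocol therapy without stopping the other. A withdrawal table restricted to AMG 176 describes only half of that. It matters most in Part 5, which has no dose-limiting toxicity endpoint, so the ordinary adverse event tables carry the tolerability assessment there.

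At stake is complete reporting. A reader of the study report could take the table as the full count of treatment withdrawals for adverse events, and nothing in the SAP says that it covers less than the protocol specified.

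**Working it through.** No power, alpha or sample-size figure is involved. The check is a comparison of text, plus one count of scope.

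**1. The two specifications.** The protocol's table covers AMG 176 or any other protocol-required therapy. The SAP's table covers AMG 176. The difference is withdrawal of azacitidine (Parts 4 and 5) or itraconazole (Part 3d) without withdrawal of AMG 176.

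**2. Does another SAP output supply the missing count?**
- SAP 9.2 (subject accountability) counts subjects who "discontinue from investigational product (including reasons for discontinuation") and those who leave the study. It has no entry for azacitidine.
- SAP 9.6.8 summarises dose modifications with reasons, but it is the AMG 176 exposure section.
- SAP 9.6.9 opens with "Descriptive statistics will be produced to describe the exposure to azacitidine, itraconazole" and then names cycles initiated, doses, cumulative and average dose, dose intensity and relative dose intensity. It gives no count of subjects who stopped and no reasons. The protocol's counterpart, 9.4.2.3.7, went further for azacitidine: "The number of cycles initiated, completed, discontinued, the duration of therapy and total dose will be summarized".
- The dose-limiting toxicity analysis does not fill the gap. Protocol 6.2.1.2 requires the event to be regarded as related to AMG 176. Under protocol 6.2.1.1 and SAP 6.7.2, a Part 4 subject who misses any planned azacitidine dose in the evaluation period without such a toxicity is not evaluable, and is replaced. Part 5 has no such endpoint.

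**3. Follow one subject.** Suppose that azacitidine is stopped for an adverse event and AMG 176 continues.
- The event enters the treatment-emergent table and, as applicable, the serious, grade 3 or higher, treatment-related and fatal tables.
- It does not enter the withdrawal table or the disposition table.
- Relative dose intensity (SAP section 5) is actual cumulative dose divided by planned cumulative dose, with the planned dose accruing over the time on study treatment. Protocol section 6 uses study treatment to include non-investigational products. On that reading the planned azacitidine dose keeps accruing while AMG 176 continues, and the ratio falls. A dose reduction or a delay would lower it too, so the ratio does not identify an adverse-event withdrawal.

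**4. Scope.** Planned enrolment (SAP 3.2) is about 60 in Part 4 and 68 in Part 5: 60 + 68 = 128 of about 219, and 128/219 = 58%. These are plans. The last count given for Part 4 is 22 subjects as of November 2022 (protocol 2.1, SAP 3.1). Part 5 was to open only after Part 4 was complete, and the SAP gives no final enrolment for either part.

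**The case against.** The strongest reply is that little information is lost, and most of that reply stands.

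- The events remain in the other safety tables, and an event that stops both drugs is counted under AMG 176. A reader might infer that azacitidine toxicity leading to discontinuation goes unreported altogether. The documents do not support that: what is missing is only the link between an event and the stopping of azacitidine alone.
- The azacitidine exposure summaries would show reduced delivery. This stands, without the cause.
- Azacitidine-only withdrawal may be uncommon. The azacitidine rules in protocol 6.2.2.3.1 work through dose reductions and cycle delays and contain no rule for permanently stopping azacitidine alone. The hepatotoxicity rules in protocol 11.7 cover AMG 176 and the other therapies together. This bears on frequency, and a restored withdrawal table would not count reductions or delays either. Protocol 7.1 still allows separate stopping, and the protocol asked for the table.
- The study ended early and a synopsis report is planned. That explains a shorter set of outputs. It does not explain this omission, because SAP section 10 names what is dropped and this is not named.
- The protocol allowed a listing in place of a table. This stands, and the fix uses it.

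Two further inferences are tempting. One is that the gap distorts the choice of dose. Protocol 4.3.4 and 11.3 rest dose decisions on the totality of data, and neither names withdrawal incidence as a criterion. The other is that the missing table would show AMG 176 making azacitidine harder to give. There is no azacitidine-alone arm, so the table could not attribute withdrawals in that way.

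**Conclusion.** The point holds as a minor, undeclared departure of the SAP from the protocol. As written, no SAP output gives the incidence of adverse events leading to withdrawal of azacitidine when AMG 176 continues, so tolerability of the combination is incompletely reported.

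The size cannot be stated as a number. A reader might take the affected group as 128 subjects, or count each missed subject as 1/24 = 4.2 percentage points in a 24-subject Part 5A cohort. Both treat planned enrolment as actual, and after early termination nothing in the documents shows that a 24-subject cohort was filled. The affected group is the subjects actually given azacitidine, and within it those who stopped azacitidine alone for an adverse event.

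Itraconazole falls under the same wording but adds almost nothing, being a 7-day interaction probe in about 11 planned subjects.

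The conclusion rests on the SAP's own definition of investigational product and on reading its output list as complete.

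**What to change.** In SAP 9.6.2, restore coverage of the other protocol-required therapies. For Parts 4 and 5, give subject incidence of adverse events leading to withdrawal of AMG 176, of azacitidine and of either drug. If few subjects are affected, a subject-level listing is enough, as protocol 9.4.2.3.2 allows. If the sponsor decides against this output, SAP section 10 should say so.

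The data should already exist. Protocol 11.4 has the investigator record the action taken for each event, and protocol 6.2.2.3 has the reason for any azacitidine dose change recorded on the case report form. One point needs checking: the documents show action taken separately by drug only on the serious adverse event contingency form. If the main event form does not separate the drugs, the recorded reason for azacitidine dose change would have to be linked to the event.

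The cost is a small amount of extra programming and output, with no new data collection expected.

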#### **9.6.3            Laboratory Test Results**

Shifts in CTCAE grades of safety laboratory parameters between baseline and the worst post-baseline value for select blood chemistry analytes (creatinine, total bilirubin, aspartate aminotransferase [AST], alanine aminotransferase [ALT], and alkaline phosphatase [ALP]) and hematology analytes (hemoglobin, platelet count, absolute neutrophil count) will be tabulated by dose level.

A summary of potential hepatotoxicity by Hy's Law will be tabulated. The criteria are defined as AST or ALT  $\geq$  3 times upper limit of normal (ULN), total bilirubin  $\geq$  2 times ULN, and ALP  $<$  2 times ULN assessed within **30** days.

**Summary statistics of troponin over time by dose level will be provided based on data availability.**

#### **9.6.4            Vital Signs**

Vital signs (systolic / diastolic blood pressure, heart rate) over time and change from baseline will be summarized. The analyses of vital signs will include summary statistics over time **for AML parts only.**

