2.3.2 Key Risks

Based on biological plausibility, nonclinical toxicity studies of AMG 176, and clinical safety experience, tumor lysis syndrome (TLS) and increased troponins have been determined to be identified risks.

Refer to Section [6.2](#) for dose modification guidelines for AMG 176 and azacitidine.

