9.4.2.3.3 Laboratory Test Results

The analyses of safety laboratory endpoints will include summary statistics over time. Shifts in grades of safety laboratory values between baseline and the worst on-study value will be tabulated by cohorts.

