## **9. Statistical Methods of Analysis**

### **9.1 General Considerations**

Descriptive statistics on continuous data will include means, medians, standard deviations and ranges, while categorical data will be summarized using frequency counts and percentages. Graphical summaries of the data may also be presented.

When data are summarized by time, the values recorded against the scheduled time points listed in the protocol will be used. When assessing minimum/maximum increases or decreases over the study, all assessments, including unscheduled assessments will be used.

For each indication, efficacy and safety data will be summarized by dose level.

For the subjects who complete the DLT period and proceed to a higher dose level or crossover to a combinational therapy cohort for the following treatment cycle, efficacy and safety will be analyzed by the initial assigned dose level.

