1. PFS (MM), EFS (AML)
2. TTR
3. BAX and caspase 3
4. Events of interest summaries
5. Antibody formation
6. Prior anti cancer therapies

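### SAP 9.6.3 cannot show how many subjects at each dose crossed the protocol's troponin cut-offs, and four of the five TLS monitoring analytes have no shift table

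*SAP*

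**What the plan says.** Protocol 2.3.2 states that "tumor lysis syndrome (TLS) and increased troponins have been determined to be identified risks". The incidence of clinically significant laboratory changes is part of the primary safety endpoint for every part except 3d (SAP 2.1), and SAP Table 4 repeats it.

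Protocol 9.4.2.3.3 plans that "Shifts in grades of safety laboratory values between baseline and the worst on-study value will be tabulated by cohorts". It names no subset of analytes.

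SAP 9.6.3 limits the shift tables to five chemistry analytes (creatinine, total bilirubin, AST, ALT and ALP) and three haematology analytes (haemoglobin, platelets and neutrophils), by dose level. For troponin it says only "Summary statistics of troponin over time by dose level will be provided based on data availability".

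SAP 9.1 has two rules on which values count:
- "When data are summarized by time, the values recorded against the scheduled time points listed in the protocol will be used".
- For minimum or maximum changes over the study, "all assessments, including unscheduled assessments will be used".

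SAP Section 10 says that the study ended early and that a synopsis report will be written. It then lists six analyses that will not be done. One is "Events of interest summaries". The shorter list of shift analytes is not among the six.

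**The concern.** For an identified risk with numerical cut-offs in the protocol, the basic safety result is the number of subjects at each dose who ever crossed each cut-off. Statistics per visit do not give that number. The SAP's rule that brings in unscheduled values applies to maxima, but no troponin maximum over the study is planned, so the rule never takes effect for troponin.

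TLS has a similar gap. Most of the analytes that define laboratory TLS have no worst-value table, and a reader of SAP Section 10 would not learn that the protocol's plan had been narrowed.

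At stake is the description of laboratory safety by dose. Troponin behaviour underlies the restriction of further investigation to doses of 240 mg/m² or less (protocol 4.1.1). Protocol 2.3.2.2 says that no concerning elevations were seen at those doses, without defining concerning. Counts by cut-off and dose would let a reader judge that statement.

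**Working it through.** The plan gives no figure to reproduce for this point. The check compares passages and adds a short illustration.

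**Step 1. TLS analytes.** Protocol Table 1-9 names five monitoring analytes: potassium, phosphorus, calcium, uric acid and creatinine. The SAP shift list contains creatinine only, so 5 − 1 = 4 are missing. The laboratory TLS definition in protocol 11.8.2 uses uric acid, potassium, phosphorus and calcium, so all 4 of its elements lack a shift table. Protocol Table 11-1 lists these four, and troponin, under chemistry, and Table 1-9 counts chemistry among the safety laboratories.

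**Step 2. Where a troponin rise would be counted by dose.** The cut-offs come from protocol 6.2.1.2.2 and 6.2.2.1. The upper reference limit (URL) is 0.04 ng/mL for women and 0.059 ng/mL for men.

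| Central troponin-I (ng/mL) | Status in the protocol | Subject count under the SAP |
|---|---|---|
| Above URL to 0.1 | Grade 1 if isolated; withholding not required | Generally none, because findings judged not clinically significant are not recorded as events (protocol 8.2.5) |
| Above 0.1 to below 0.78 | Withholding criterion | Adverse event tables if reported (SAP 9.6.2); dose modifications with reasons (SAP 9.6.8) |
| 0.78 or more | Grade 3; listed for permanent discontinuation; DLT criterion | As above, plus DLT output if related and normally within the DLT period |

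No row has a count taken from the laboratory data themselves. Because the URL depends on sex, a visit maximum between 0.04 and 0.059 does not even show whether the limit was crossed.

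**Step 3. Whether visit statistics can yield incidence.** Assume 6 subjects and 5 scheduled visits, with all values 0.02 ng/mL except for peaks of 0.30 at three visits. In pattern A three different subjects peak once each. In pattern B one subject peaks three times.

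- Mean at each peak visit, both patterns: (0.30 + 5 × 0.02)/6 = 0.40/6 = 0.0667.
- Median: 0.02 in both.
- SD: √{[(0.30 − 0.0667)² + 5 × (0.02 − 0.0667)²]/5} = 0.114 in both.
- Maximum: 0.30 in both.
- Subjects ever above 0.1: A = 3/6 (exact 95% CI 12% to 88%); B = 1/6 (0.4% to 64%).

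The same holds in the band that event tables generally miss. With peaks of 0.1 instead of 0.30, each peak-visit mean is (0.1 + 5 × 0.02)/6 = 0.0333, with median 0.02 and maximum 0.1 in both patterns. The number of subjects ever above the URL is again 3/6 against 1/6.

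The maximum does reveal that a scheduled peak occurred. It does not say how many subjects had one, and an unscheduled peak does not enter at all.

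**The case against.** The strongest reply is that other outputs already cover the serious cases. Protocol 8.2.5 also says that laboratory changes needing treatment or an adjustment of therapy are adverse events. Troponin above 0.1 ng/mL is a withholding criterion. Laboratory TLS criteria met within 24 hours of the first dose or an escalation stop further dosing until resolution (protocol 6.1.4.1). Such cases should therefore reach the adverse event tables by dose level and, where dosing changed, the dose-modification summary. Grade 3 troponin-I and clinical TLS are DLT criteria for all subjects (protocol Table 6-1). Much of this stands. It limits the gap but does not close it: capture depends on the investigator reporting the event, DLTs require relatedness, and the DLT table may be replaced by subject-level data when events are few (SAP 9.6.2).

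A reader might also infer more than the documents support:

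- **That troponin peaks are left out altogether.** SAP 9.1 reports ranges, so a scheduled peak appears as a visit maximum, and cardiac tests are scheduled often around dosing.
- **That all TLS analytes are omitted.** Creatinine is included.
- **That neither risk has any incidence by dose.** Event and DLT incidence remain.
- **That dropping events of interest removed TLS and troponin.** The documents do not define those events, and the removal is declared with a reason.
- **That the evidence for the 240 mg/m² limit would go unreported.** Protocol 4.1.1 cites troponin DLTs in 2 of 8 subjects at 360 mg/m², and DLTs remain reported. Dosing decisions rest on the dose-level review team's review of all cumulative data, not on these tables.

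It is also arguable whether protocol 9.4.2.3.3 promised troponin shifts, because Table 1-9 lists cardiac tests separately from safety laboratories. The undeclared narrowing is firmer for the four chemistry analytes.

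**Conclusion.** The concern holds in limited form. No planned table counts subjects by maximum troponin at any of the three cut-offs, and unscheduled troponin values are excluded from the only planned summary. Four of the five TLS monitoring analytes, and all four elements of laboratory TLS, lack the worst-grade shift that protocol 9.4.2.3.3 planned without restriction; Section 10 does not say so. The least covered group is subjects with isolated rises above the URL up to 0.1 ng/mL. Above that, coverage exists but passes through investigator reporting.

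The illustration uses assumed values and shows only that incidence cannot be recovered from visit statistics. The documents do not show how many peaks fell at unscheduled draws, nor whether the SAP means central troponin-I or local troponin I or T. The point changes no dosing rule. For a terminated phase 1 study with a synopsis report it is a cheap improvement, not a must-fix.

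**What to change.** Make three changes to the SAP:

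1. In 9.6.3, add a table of each subject's maximum post-baseline central troponin-I, scheduled and unscheduled, by part, schedule and dose. Use the protocol's categories: at or below the sex-specific URL; above URL to 0.1; above 0.1 to below 0.78; 0.78 ng/mL or more. SAP 9.6.6 already does this for QTcF, with maximum post-baseline categories that include unscheduled assessments, so the format exists. Keep the over-time summary as a supplement.
2. In 9.6.3, add worst-value shifts for potassium, phosphorus, calcium and uric acid. State the direction used in protocol 11.8.2: high for potassium, phosphorus and uric acid, low for calcium.
3. In Section 10, list whatever narrowing from protocol 9.4.2.3.3 remains.

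The data are already collected. The cost is SAP wording and a few extra tables in a synopsis report.
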